## 5.4.13 Immunogenicity

ADA responses in the form of anti-SPV-T3a-RTA and anti-WT1-RTA antibodies will be evaluated using serum samples obtained at baseline and at Days 7, 14, 28, 90, and 180 following initiation of T-Guard treatment. Antibody levels will be described using descriptive statistics at each time point. Changes in levels from baseline will be evaluated using Wilcoxon signed rank tests.

## 5.4.14 Subgroup Analyses of Day 28 CR Rate

In a secondary analysis of the primary endpoint, the CR rate at Day 28 will be evaluated separately by age group (adulthood vs. adolescence), aGVHD grade, and DRI. Point estimates and 95% Wilson score or Clopper-Pearson CIs will be provided for each subgroup, as appropriate.

# 5.5 ANALYSIS OF EXPLORATORY ENDPOINTS

The analysis of exploratory endpoints will be based on the primary analysis population.

## 5.5.1 Corticosteroid Dose

The current steroid dose being administered (measured in prednisone equivalent) will be described by mean, median, range, and quartiles at baseline and Day 28 and 56 post T-Guard initiation.

# 5.5.2 Near Complete Response (Near CR)

The proportion of patients with a near CR (having isolated stage 1 skin GVHD) will be estimated at Day 7, 14, 28, and 56 using sample proportions and 95% Wilson score or Clopper-Pearson Cls, where appropriate.

Estimates and 95% CIs of OS at Day 180 post-initiation of T-Guard treatment will also be obtained from the Kaplan-Meier estimator separately for two subsets of patients: those that attain a near CR or CR, and those who fail to reach a (near) CR.

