to have partial response (PR) by current staging, likely have superior outcomes compared to those patients with persistence of visceral aGVHD. We hypothesize this patient group, with visceral and skin GVHD who meet the criteria for CR except for persistent, low volume skin rash (what we will call near-CR), will have identical outcomes compared to those patients with CR. The response to primary therapy is of central importance, as responses correlate with post-HCT survival.

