# 1.3.3 Justification for the Proposed Dose Regimen for this Phase III Clinical Trial Using T-Guard as First Line SR-GvHD Treatment

The proposed dose for the T-Guard Phase 3 study is  $4 \text{ mg/m}^2$  / dose q 48 hours x 4 doses. This dose is based on the following data:

In the investigator-initiated dose-escalation study (van Oosterhout, van Emst et al. 2000, van Oosterhout, van Emst et al. 2001) it was determined that the second dose level of 4 mg/m^2/dose q 48 hours x 4 doses delivered positive biological and clinical responses, without inducing any severe acute toxicities.

PK analysis showed that the 4 mg/m^2 x 4 doses schedule led to T-Guard *in vivo* serum  $C_{max}$  of around 1.5 µg/ml (~10^-8M). On basis of *in vitro* experiments, the  $C_{max}$  attained results in a 60-80% occupation of the target antigens CD3 and CD7. It has been shown in *in vitro* studies that this concentration is very effective in specifically eliminating antigen-positive target cells by RTA-based immunotoxins (Derocq, Laurent et al. 1987, Preijers, De Witte et al. 1988, Preijers, Tax et al. 1988, Herrera, Farah et al. 2000).

Given the 50% Day 28 CR rate observed in the T-Guard Phase 1/2 study, it could be argued that the clinical benefit may be further optimized by administering a higher T-Guard dose. When judging the response rate, though, consideration is given to the high incidence of serious comorbidities in this severely ill population. Four of the 20 patients of the T-Guard Phase 1/2 study died before Day 28 due to comorbidities; two patients died from sepsis (non- treatment related), one patient died in the treatment week with uncontrolled viral infections, and another patient had vanishing bile duct syndrome with very rare aberrant bile ducts at treatment start suggestive for co-existing liver disease of different etiology. When these four patients are censored, the Day 28 response rate increases to 63% CR (10/16) and 75% ORR (12/16), respectively. In the Phase 1/2 study, the adverse events judged to be potentially treatment-related were clinically manageable and included 7 mild cases (35%) and 1 moderate case (5%) of CLS.

To put the currently applied T-Guard dose in perspective, the Maximum Tolerated Dose as

[figure not shown]

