# **3 STUDY ENDPOINTS**

## 3.1 ACUTE GVHD RESPONSE DEFINITIONS

Scoring of aGVHD response on a given day is in comparison to the patient's aGVHD staging on the day of initial T-Guard treatment. Organ staging will be assessed using the Harris criteria (Appendix C) and response will be scored as defined below:

Complete response (CR) is defined as a score of 0 for the GVHD staging in all evaluable organs. For example, for a response to be scored as CR, the patient must still be in CR on that day and have had no intervening additional systemic therapy for treatment of aGVHD.

Near-CR is defined as a score of 0 for the GI and/or liver GVHD staging, but with persistence of skin rash at less than 25% BSA (Stage 1 skin GVHD). Near CR can only occur in patients with both visceral and skin aGVHD.

Partial response (PR) is defined as improvement in one or more organs involved with GVHD symptoms without progression in others. For example, for a response to be scored as PR, the patient must still be in PR on that day and have had no intervening additional systemic therapy for treatment of aGVHD.

Mixed response (MR) is defined as improvement in one or more organs with deterioration in another organ manifesting symptoms of GVHD or development of symptoms of GVHD in a new organ.

No response (NR) is defined as absence of any improvement or progression as defined.

Patients receiving additional systemic therapy will be classified as non-responders.

Progression is defined as deterioration in at least one organ without any improvement in others.

Loss of CR or near-CR is defined as progression of aGVHD symptoms requiring additional systemic therapy; death; or if the patient develops new target organ symptoms that could qualify as being from either aGVHD or cGVHD (if the new symptoms are only associated with cGVHD then this is not considered a loss of CR).

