#### 3.4.1.2 Overall Survival (OS)

OS will be assessed at Days 90 and 180 post initiation of T-Guard treatment. An event for this analysis is death from any cause and time will be calculated from initiation of T-Guard treatment until date of death.

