# 3.5.1.1 Near Complete Response (Near CR)

Near CR is defined as having stage 1 skin GVHD only (persistence of skin rash at less than 25% BSA) with a score of 0 in other target organs. The proportion of patients with a near CR will be evaluated at Day 7, 14, 28, and 56 post-initiation of T-Guard treatment. The OS rates at Day 180 will also be described for patients that attain a near CR or better and those who do not.

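### Day 180 survival by (near-)CR attainment is counted from T-Guard initiation with no landmark, so the estimates carry immortal-time bias in favour of responders

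*Combined protocol and SAP*

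**What the plan says.** Section 5.5.2 states: "Estimates and 95% CIs of OS at Day 180 post-initiation of T-Guard treatment will also be obtained from the Kaplan-Meier estimator", separately for two subsets, "those that attain a near CR or CR, and those who fail to reach a (near) CR". The endpoint text in Section 3.5.1.1 matches it: "The OS rates at Day 180 will also be described for patients that attain a near CR or better and those who do not". Section 3.4.1.2 fixes the OS clock: "time will be calculated from initiation of T-Guard treatment until date of death".

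The near-CR proportion "will be estimated at Day 7, 14, 28, and 56 using sample proportions", all days after time zero. The OS sentence itself gives no day for attaining the response. No landmark, time-dependent or multi-state handling is described for it.

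Two other places bear on the grouping. Section 1.1 hypothesizes that near-CR patients "will have identical outcomes compared to those patients with CR". Section 3.1 restricts the category: "Near CR can only occur in patients with both visceral and skin aGVHD". Sections 3.5.1.1 and 5.5.2 describe near-CR as stage 1 skin disease alone and do not repeat that restriction.

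**The concern.** Group membership is decided by something observed after the survival clock has started. Being alive at the response assessment is a condition of entering the responder group, so the time from Day 0 to response is death-free there by construction. Deaths before any response all go to the other group. This happens whether response is read at Day 28 or at any visit.

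Early death is frequent in this population. Section 1.3.3 reports: "Four of the 20 patients of the T-Guard Phase 1/2 study died before Day 28". Section 5.2.2 expects 15% mortality by Day 30. Two survival estimates with confidence intervals, shown side by side, invite the reading that reaching (near-)CR predicts survival. This analysis would give that impression even if it were untrue.

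A lesser point is that near-CR and CR form one group in the only planned survival analysis by near-CR. The display therefore says nothing about the Section 1.1 hypothesis and could hide a departure from it.

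**Working it through.** The documents give no figure for this analysis, so there is none to reproduce. The check asks what the planned estimates would show if response had no effect on survival.

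**Inputs**
- q, death before Day 28: 4/20 = 20% in Phase I/II (Section 1.3.3). The expected Day 30 mortality is 15% (Section 5.2.2).
- R, share of all patients in response at Day 28: 10/20 = 50% CR in Phase I/II (Section 1.3.2.3). This counts CR only, because no near-CR rate is given.
- S, Day 180 OS: 60% in Phase I/II and 29% in that study's historical data (Section 1.3.2.3).
- Assumption: among patients alive at Day 28, survival to Day 180 is the same with or without a response, namely S/(1 − q).

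**Response fixed at Day 28, clock from Day 0**
- Responders are all alive at Day 28, so OS = S/(1 − q).
- Non-responders make up 1 − R of patients, of whom 1 − q − R are alive at Day 28, so OS = [(1 − q − R)/(1 − R)] × S/(1 − q).
- Gap = [S/(1 − q)] × [q/(1 − R)].

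Phase I/II figures: responders 0.60/0.80 = 75%; non-responders (0.30/0.50) × 0.75 = 45%; gap 30 points. With a Day 28 landmark both groups have 12/16 = 75%, a gap of 0.

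With q = 15%, R = 50%, S = 60%: 0.60/0.85 = 71% against (0.35/0.50) × 0.706 = 49%, a gap of 21 points.

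Range for q 10–20%, R 30–60%, S 29–70%:
- Smallest (q = 10%, R = 30%, S = 29%): (0.29/0.90) × (0.10/0.70) = 4.6 points.
- Largest (q = 20%, R = 60%, S = 70%): (0.70/0.80) × (0.20/0.40) = 43.8 points.

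The gap rises with R, so counting near-CRs as well would widen it.

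**Response counted at any of Days 7, 14, 28, 56**

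Assume 20/15/15/10% of patients would respond at those visits independently of survival, with piecewise exponential survival through S(28) = 0.80 and S(180) = 0.60. Then S(7) = 0.946, S(14) = 0.894 and S(56) = 0.759.
- Attainers: 0.20 × 0.946 + 0.15 × 0.894 + 0.15 × 0.80 + 0.10 × 0.759 = 0.519 of patients. Their OS is 0.60 × 0.60/0.519 = 69%.
- Others: 0.40 × 0.60/0.481 = 50%. The gap is 19 points.

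A simulation of 400,000 patients per setting, with Day 30 mortality 15–30%, Day 180 OS 29–60% and underlying response 50–70%, gave gaps of 7 to 36 points. At 15%, 60% and 60% it gave 67% against 52% as planned, 70% in both groups with a Day 28 landmark, and 75% in both with a Day 56 landmark. Landmark gaps were at most 0.7 points, which is simulation noise.

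**Near-CR against CR**

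Assume about 23 CRs (50% of 47), 2 to 10 near-CRs and Day 180 OS of 75%. The 95% half-width for the difference is 1.96 × √[0.75 × 0.25 × (1/23 + 1/n)], or 63 points at n = 2 and 32 points at n = 10. If near-CR OS were 45% and CR OS 75%, the pooled figure would be (23 × 0.75 + n × 0.45)/(23 + n), that is 73% at n = 2 and 66% at n = 10. Pooling would hide the difference, but separate estimates would be very imprecise.

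**The case against.** The strongest reply is that this is one exploratory estimate in a study whose analysis Section 5.1 calls descriptive. No test or contrast between the groups is specified, only separate estimates with confidence intervals. That stands and limits the importance, but it does not remove a bias whose direction is known in advance.

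Several stronger readings are tempting, and the documents do not support them:
- A reader might infer that response at any time counts. The visit days in Section 5.5.2 belong to the near-CR proportion, and the OS sentence names no day. The defect is that the day is unspecified, and the bias arises under either reading.
- A reader might infer that every early death lands in the non-responder group. Only deaths before a response do. In the any-visit example, 0.20 × (0.946 − 0.80) + 0.15 × (0.894 − 0.80) = 4.3% of patients respond and then die by Day 28, and they count as attainers.
- A reader might infer that the plan fails an objective to compare near-CR with CR. That hypothesis is background in Section 1.1. The near-CR objective in Section 2.3.3 is only to estimate its rate, and describing OS for near-CR or better is a legitimate summary of a broader category.
- A reader might infer that an unchanged patient with stage 1 skin disease alone would count as near-CR. Section 3.1, which governs response definitions, already excludes this. The later sections need a cross-reference, although Section 2.4.1 sets no minimum grade, so such patients could be enrolled.

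It is also fair to say that a Day 28 landmark answers a different question from ever attaining a response.

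**Conclusion.** The point holds. As written, Sections 5.5.2 and 3.5.1.1 give survival estimates that are immortal-time biased in favour of responders, whether response is taken at Day 28 or at any visit. With no true association, the false gap is 30 points on the Phase I/II figures and roughly 5 to 44 points over plausible inputs. The size rests on early mortality, response share, response timing and Day 180 survival. The documents report neither a near-CR rate nor OS by response, so no single value should be relied on. The direction does not depend on these choices.

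The primary Day 28 CR conclusion, the futility rule and the sample size of 47 do not use this analysis and are unaffected. Pooling near-CR with CR, and the missing cross-reference to Section 3.1, are secondary matters of presentation.

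**What to change.** Amend Sections 3.5.1.1 and 5.5.2 as follows:
- Among patients alive at Day 28, classify by Day 28 response status and estimate Kaplan-Meier OS from Day 28 to Day 180. Repeat with a Day 56 landmark if wanted.
- Show CR, near-CR and neither as three groups. State that this is description only, because the near-CR group will be small and its estimate imprecise.
- Cross-refer the near-CR definition to Section 3.1, so that the visceral-plus-skin requirement applies.

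The cost is wording. Acute GVHD staging is already collected at Days 28 and 56 (Section 4.3.2), and Section 5.4.1 already identifies the patients in CR at Day 28. Patients who die before Day 28 leave this analysis but stay in overall OS. Later responders, and patients who lost an earlier response, are classed by their Day 28 status. The landmark removes the immortal-time artefact but not confounding by disease severity, so any remaining difference should not be read as an effect of response.

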## 5.5.3 Discontinuation of Systemic Steroids

The proportion of patients that are free of systemic steroids above physiological replacement at Day 180 post-T-Guard initiation will be described.

## 5.5.4 CMV Reactivation

Among patients that were CMV positive at enrollment, the cumulative incidence of initiation of systemic treatment for CMV-reactivation will be described using the Aalen-Johansen estimator, with death treated as a competing risk. An estimate and 95% CIs of the cumulative incidence of CMV reactivation will be provided at Day 180 post-initiation of T-Guard.

# 5.5.5 EBV-associated Lymphoproliferative Disorder

The cumulative incidence of either EBV-associated lymphoproliferative disorder or EBV reactivation requiring therapy with rituximab will be described using the Aalen-Johansen estimator, with death treated as a competing risk. An estimate and 95% CIs of the cumulative incidence of EBV-associated lymphoproliferative disorder/EBV reactivation will be provided at Day 180 post-initiation of T-Guard.

# 5.5.6 Incidence of Investigational Medical Product (IMP)-related Serious Adverse Events (SAEs)

SAEs that are deemed to be related to T-guard treatment will be summarized by type, frequency, and number of patients affected.

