#### Preferred Term (≥5 Patients in Total) for TEAEs, Overall Study

System organ class/ Preferred term	Total (N=20) n (%)
Hypoalbuminemia	8 (40.0%)
Hyperglycemia	7 (35.0%)
Hypokalemia	5 (25.0%)
Hypophosphatasemia	5 (25.0%)
General disorders and administration site conditions	16 (80.0%)
Edema peripheral	8 (40.0%)
Pyrexia	8 (40.0%)
Fatigue	6 (30.0%)
Gastrointestinal disorders	15 (75.0%)
Nausea	5 (25.0%)
Investigations	13 (65.0%)
Blood bilirubin increased	6 (30.0%)
White blood cell count decreased	5 (25.0%)
Musculoskeletal and connective tissue disorders	13 (65.0%)
Muscular weakness	5 (25.0%)
Myopathy	5 (25.0%)
Vascular disorders	12 (60.0%)
Capillary leak syndrome	8 (40.0%)
Blood and lymphatic system disorders	11 (55.0%)
Anemia	6 (30.0%)
Thrombocytopenia	6 (30.0%)
Nervous system disorders	11 (55.0%)

In total 29 Serious Adverse Events (SAE) were reported in 14 patients (Table 1-2). Of those SAEs, 23 were reported as severe, 4 as moderate and 2 as mild. Eight (8) patients died during the course of the trial. The causes of death were determined to be refractory aGVHD, infections or the combination of the two. All deaths were reported as not related to T-Guard. No deaths occurred before 6 months (Day 180) due to relapse of the underlying disease.

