# 2.3.3 Exploratory Objectives

- 1. Describe corticosteroid-dose (measured in prednisone-equivalent) at baseline, Days 28 and 56 post initiation of T-Guard treatment.
- 2. Estimate the rate of near-CR (i.e. CR in GI and Liver with only Stage 1 Skin) at Days 28 and 56 post initiation of T-Guard treatment.
- 3. Describe discontinuation of systemic steroids by Day 180 post initiation of T-Guard treatment.
- 4. Estimate the incidence of CMV reactivation requiring treatment by Day 180 post initiation of T-Guard treatment.
- 5. Estimate the incidence of EBV-associated lymphoproliferative disorder or EBV reactivation requiring treatment with rituximab by Day 180 post initiation of T-Guard treatment.
- 6. Describe the incidence of IMP related SAEs.
- 7. Evaluate T-cell subsets and NK-cells at baseline and at Days 0, 2, 4, 6 (just prior to and 4 hours after each T-Guard infusion) and then subsequently at Days 14, 28, 56, and 180.
- 8. Evaluate aGVHD Biomarkers at baseline and at Days 7, 14 and 28 post initiation of T- Guard treatment.
- 9. Describe changes in patient-reported outcomes (PROs) from baseline to Days 28, 56 and 180 post initiation of T-Guard treatment.

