# 4.4.1 Definitions

Adverse Event: An AE is any untoward medical occurrence in a patient administered an investigational product or has undergone study procedures and which does not necessarily have a causal relationship with this treatment. An AE can therefore be any unfavorable and unintended sign (including an abnormal laboratory finding), symptom, or disease that is temporally associated with the use of a medicinal (investigational) product, whether or not related to the medicinal (investigational) product.

An abnormality identified during a medical test (e.g., laboratory parameter, vital sign, ECG data, physical exam) should be defined as an AE only if the abnormality meets 1 of the following criteria:

- Induces clinical signs or symptoms.
- Requires active intervention.
- Requires interruption or discontinuation of study medication.
- The abnormality or investigational value is clinically significant in the opinion of the investigator.

**Serious Adverse Event:** An SAE, as defined by per 21 CFR 312.32, is any adverse event that results in one of the following outcomes, regardless of causality and expectedness:

- Results in death
- Is life-threatening. Life-threatening means that the person was at immediate risk of death from the reaction as it occurred, i.e., it does not include a reaction which hypothetically might have caused death had it occurred in a more severe form.
- Requires or prolongs inpatient hospitalization (i.e., the event required at least a 24hour hospitalization or prolonged a hospitalization beyond the expected length of stay). Hospitalization admissions and/or surgical operations scheduled to occur during the study period but planned prior to study entry are not considered SAEs if the illness or disease existed before the person was enrolled in the trial, provided that it did not deteriorate in an unexpected manner during the trial (e.g., surgery performed earlier than planned).
- **Results in persistent or significant disability/incapacity**. Disability is defined as a substantial disruption of a person's ability to conduct normal life functions.
- Is a congenital anomaly or birth defect; or

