## 4.4.3 Classification of Adverse Events by Relationship to Investigational Product

The relationship of each reported event to the study treatment will be assessed by the Investigator; after careful consideration of all relevant factors such as (but not limited to) the underlying study indication, coexisting disease, concomitant medication, relevant history, pattern of the SAE, temporal relationship to any study treatment interventions and dechallenge or rechallenge according to the following guidelines:

- Possibly, Probably, or Definitely Related: there is a reasonable possibility that the study treatment caused the event. A relationship of possibly, probably or definitely related to the investigational product is considered related for the purposes of regulatory authority reporting.
- Unlikely, or Not Related: There is no reasonable possibility that the investigational product caused the event. An unlikely or not related relationship to the investigational product is not considered related for the purposes of regulatory authority reporting. One or more of the following criteria apply:

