# 4.4.4 Required Adverse Event Reporting

Any unanticipated SAEs from time of enrollment through the study defined follow up are required to be reported following the BMT CTN Administrative MOP Chapter 6. Additionally, any grade 4 anticipated event not collected on the calendar-driven toxicity or specified event- driven form must **also** be reported through the expedited AE reporting system in Advantage eClinical. Chapter 6 of the BMT CTN MOP defines reporting based on the terms Unexpected and Expected; however, for this study, the reporting will be based on the terms Unanticipated and Anticipated All adverse events, including SAEs, must be reported from the 1st dose of T- Guard through 30 days after the last dose. In addition, any SAEs occurring after that 30-day period, but assessed as related to the investigational product, must be reported. All SAEs are to be followed up until resolved, judged to be no longer clinically significant, or until they become chronic to the extent that they can be fully characterized.

Infections are collected separately in eClinical as this is a study endpoint; however, should an infection meet the SAE criteria the infection must also be reported following the SAE reporting criteria outlined above.

GVHD and underlying disease relapse events are also collected separately in eClinical because they are part of the endpoint analysis. Events of GVHD and underlying disease relapse are not to be reported as AEs/SAEs for this study.

The Sponsor has a list of events classified as Special Situations. These events are 1) medication error, 2) overdose and 3) pregnancy. These events must be reported following the reporting for SAEs.

SAEs that require reporting will be reported through an expedited AE reporting system via an EDC. All SAEs, as well as Special Situations, must be reported within 24 hours of knowledge of the event. Events entered in EDC will be reported using NCI's CTCAE Version 5.0. If there are network outages, a paper copy of the AE form must be completed and emailed to Emmes to initiate Sponsor review. Once the system is available, the event information must be entered into the system.

Anticipated AEs will be reported using NCI's CTCAE Version 5.0 at regular intervals as defined on the Form Submission Schedule, including calendar-driven eCRFs (e.g., Toxicity and GVHD) or event-driven eCRFs (e.g., Relapse/Progression, Infection, Secondary Graft Failure and Death).

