#### 5.1.2 Randomization and Blinding

No randomization or blinding will occur as this is a single arm open label trial.

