#### 5.4.11 Incidence of Toxicities

The frequency of Grade 3-5 toxicities per CTCAE version 5 occurring from the initiation of T-Guard treatment until 28 days post-last dose will be tabulated by organ system. The maximum severity of reported toxicities during that period will also be summarized.

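### The statistical chapter plans no all-cause SAE summary for the final analysis; its only SAE analysis covers events the unblinded investigator judges related to T-Guard

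*Combined protocol and SAP*

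**What the plan says.** - **Objective.** Exploratory objective 6 in Section 2.3.3 reads "Describe the incidence of IMP related SAEs". The synopsis has the same item.
- **Analysis.** Sections 3.5.1.5 and 5.5.6 use one sentence for the endpoint and its analysis: "SAEs that are deemed to be related to T-guard treatment will be summarized by type, frequency, and number of patients affected". Chapter 5 has no other SAE analysis.
- **Who applies the filter.** Section 4.4.3: "The relationship of each reported event to the study treatment will be assessed by the Investigator". An event rated possibly, probably or definitely related counts as related.
- **Design.** Section 5.1.2: "No randomization or blinding will occur as this is a single arm open label trial".
- **What is collected.** Section 4.4.1 defines an SAE "regardless of causality and expectedness". Section 4.4.4 adds: "All adverse events, including SAEs, must be reported from the 1st dose of T- Guard through 30 days after the last dose". After that window, SAEs assessed as related must still be reported. Unanticipated SAEs are reported from enrollment through study follow-up. GVHD and relapse events are not reported as AEs or SAEs.
- **Nearest all-cause outputs.** Section 5.4.11 tabulates by organ system "The frequency of Grade 3-5 toxicities per CTCAE version 5 occurring from the initiation of T-Guard treatment", up to 28 days after the last dose. Section 5.4.10 does the same for Grade 2-3 infections. Section 4.4.4 also gives the DSMB semi-annual summaries of all reported SAEs.

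**The concern.** The final analysis applies an attribution filter that data collection does not. With no control arm there is no background rate against which to check an investigator's causality call, and the investigator knows that every patient received T-Guard. Infection is the hardest case: Section 1.4 describes profound T-cell and NK-cell depletion by the drug, while Sections 1.1 and 1.2.2 name serious infection as a consequence of GVHD and its immunosuppression.

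The Phase I/II account in Section 1.3.2.4 shows what a related-only presentation leaves out. The causes of death were refractory aGVHD, infection or both, and "All deaths were reported as not related to T-Guard". The text refers to Table 1-2 when it reports 29 SAEs, but that table lists only adverse events potentially related to treatment. It does not mark which were serious, and it shows no infection and no Grade 5 event. A reader cannot tell what the 29 SAEs were. Section 5.5.6 would repeat that presentation in a trial that Section 1.3.3 describes as pivotal and meant to confirm safety as well as efficacy.

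**Working it through.** **Step 1. Is there an all-cause SAE table anywhere in the planned final analysis?**

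| Output | Relatedness filter | Identifies SAEs | Part of planned final analysis |
|---|---|---|---|
| Related SAEs (5.5.6) | Yes | Yes | Yes |
| Grade 3-5 toxicities (5.4.11) | No | No | Yes |
| Grade 2-3 infections (5.4.10) | No | No | Yes |
| OS and NRM (5.4.2, 5.4.5) | No | No (deaths only) | Yes |
| Day 30 mortality and Grade 4 or higher CLS (5.2.2) | No | No | No, sequential monitoring |
| DSMB summaries of reported SAEs (4.4.4) | No | Yes | No, semi-annual monitoring |

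No row combines no filter, identification of SAEs and final analysis. That is the gap.

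**Step 2. Phase I/II figures (Section 1.3.2.4).**
- Severity split: 23 severe + 4 moderate + 2 mild = 29, which matches the stated total.
- Patients with at least one SAE: 14/20 = 70%. The Clopper-Pearson limits are the 2.5% quantile of Beta(14, 7) = 45.7% and the 97.5% quantile of Beta(15, 6) = 88.1%.
- Deaths: 8/20 = 40% (exact 95% CI 19-64%). None was called related.

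**Step 3. Illustration for 47 patients, assuming Phase I/II rates carry over.**
- Patients with an SAE: 0.70 × 47 = 32.9, about 33. At the CI limits: 0.457 × 47 = 21.5 and 0.881 × 47 = 41.4, so about 21 to 41.
- SAEs: 29/20 × 47 = 68.15, about 68.
- SAEs omitted from a related-only table: (1 − s) × 68.15, where s is the related share. The documents do not give s, so a range is shown.

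| Assumed related share s | SAEs omitted, of about 68 |
|---|---|
| 10% | 61 |
| 25% | 51 |
| 50% | 34 |
| 75% | 17 |

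**Step 4. Could the toxicity table stand in?** In Phase I/II, (4 + 2)/29 = 21% of SAEs were mild or moderate. If mild and moderate mean Grades 1-2, which is an assumption, SAEs of that kind fall outside a Grade 3-5 table. The other 23/29 = 79% could enter it, but would not be identified as serious. The 21% is not an estimate of SAEs lost to all tables: some of the six may have been related, and any that were infections could enter the infection table, which uses a different grading scale.

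**The case against.** The strongest reply is that related SAEs are one exploratory endpoint and the main safety evidence carries no attribution filter. Day 30 mortality and Grade 4 or higher CLS are monitored monthly, and toxicities, infections, OS and NRM are all analysed regardless of cause. The filter is also wide, since possibly related counts as related. The output is labelled as IMP-related and is not offered as the overall SAE rate. The DSMB sees all reported SAEs. All of this stands, and it limits the importance of the point. It does not supply a final all-cause SAE table.

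Four stronger readings are tempting but not supported:
- **A reader might infer that most SAEs would go unreported.** The related share is never stated, and many unrelated SAEs would be counted in the toxicity or infection tables, though not as SAEs.
- **A reader might infer that the safety conclusion rests on a subjective filter.** Only the SAE summary does.
- **A reader might infer from the eight Phase I/II deaths that deaths would be hidden.** Every death enters OS, and deaths by Day 30 enter the mortality monitoring. What could be missing is a fatal SAE from the SAE table.
- **A reader might infer that an all-cause SAE rate is needed for comparison with historical data.** The documents give no historical-control SAE rate. The exclusion of GVHD and relapse events would limit such a comparison in any case.

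The projection to 47 patients is also loose: the SAE window and exclusions of the Phase I/II study are not given, so its 70% may not be comparable.

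**Conclusion.** The point holds as a gap in planned reporting. The synopsis, objective 6, Section 3.5.1.5 and Section 5.5.6 all restrict the final SAE analysis to events judged related by an unblinded investigator, with no control arm, although all-cause SAEs (other than GVHD and relapse) are collected to 30 days after the last dose. This follows from the text and rests on no calculation.

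The size cannot be fixed. If Phase I/II rates carry over, about 33 of 47 patients would have an SAE, and a related-only table would omit about 17 to 61 of some 68 events as the related share falls from 75% to 10%. Both the carry-over and that range are assumptions. No primary or key secondary endpoint, futility boundary or safety guideline is affected. This is an inexpensive improvement that makes the SAE report less dependent on attribution; it is not a flaw that undermines the trial's safety assessment.

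**What to change.** Amend the synopsis item, Section 2.3.3 objective 6, Section 3.5.1.5 and Section 5.5.6 together, so that objective, endpoint and analysis agree:

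- Tabulate all SAEs from first dose to 30 days after the last dose regardless of attribution, by type and grade and including fatal SAEs, with number and percentage of patients in the primary analysis population.
- Give an exact (Clopper-Pearson) 95% CI for the proportion of patients with at least one SAE.
- Show the related subset alongside.
- List later related or unanticipated SAEs separately, because all-cause collection ends at 30 days after the last dose.
- Add a footnote that GVHD and relapse events are excluded under Section 4.4.4.

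The cost is one additional table, one listing and matching wording in four places. The data are already collected and already summarised for the DSMB, so no new visits, samples or patients are needed.
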